5.3.2 Head and Neck Specialist

- (1) Head and Neck Specialists will be recruited based on recommendations from enrolled dental practitioners. Specialists are enrolled in the study so that each participating dental practice location has coverage by a specialist.

- (2) Additionally, participating specialists will be compensated for the time required to complete research activities, receiving \$120.00 for each visit completed.

5.3.3 Patient

5.3.3.1 Recruitment

- (1) A convenience sampling approach will be used to enroll patients, with an emphasis on enrollment of the first 1,000 patients who meet the eligibility criteria from among the approximately 30 practice locations, with an enrollment of approximately 25-50 patients per practitioner. The initial recruitment for screening may be led by other practice staff (e.g., dental hygienists, dental assistants).
- (2) In order to avoid a situation where enrollment is cut off in the middle of a business day, up to 1,200 enrollments may be allowed. Enrollment will be halted within approximately 48 hours of reaching the target of 1,000 patients, total.
- (3) The entire enrollment period is estimated to be approximately 3-6 months.
- (4) Each practitioner is expected to enroll approximately 25-50 patients.
 - a. To meet this recruitment goal, each practitioner should expect to enroll approximately 1-3 patients per day.
 - b. Some practitioners will enroll at a faster rate than others; practitioners are expected to enroll patients according to their patient volume.
- (5) Participant diversity will be assessed in real-time.
- (6) Practices will be expected to participate in enrollment until the recruitment goal (approximately 25-50 patients per practitioner) is met.

Part I, Oral HPV Screening

- (7) All study-related documentation, including consent forms (Appendices B and J) and electronic surveys, will be available in English and Spanish.
- (8) Study procedures, including informed consent (Appendix A), will be conducted by means of a web-based computer application; all surveys will be administered on a touch screen tablet.
- (9) Educational materials with frequently asked questions (FAQ) and resources related to HPV infection and oral cancer will be provided to each participating practice for distribution to patients at the time of enrollment. See Appendix K: *Oral HPV FAQ Documents*.
- (10) Participants who are not selected to provide an oral rinse sample will be paid \$10.
- (11) Participants who provide an oral rinse sample will be paid \$20.

Part II, Oral Cancer Screening Examination/Follow-up Study

- (12) All patients with a positive result for high-risk oral HPV will be offered the opportunity to participate in the follow-up study. See Appendix F: *High-risk Oral HPV Results Notification Script, Positive*.
- (13) Soon after the patient has been notified about the positive High-risk HPV test result, follow-up study consent will be obtained by the RC via telephone with an IRB-approved script (Appendix H).
- (14) All follow-up appointments will be scheduled in concordance with the patients' and practices' schedules. Scheduled follow-up appointments include:
 - a. Blood draw (clinical/local laboratory, community hospital, participating dental practice, mobile nursing service, or Head and Neck Specialist's practice);
 - b. Oral cancer screening examination (participating Head and Neck Specialist's practice); and
 - c. Final study visit consisting of the electronic oral cancer risk factor survey (Appendix J) and repeat oral rinse (participating dental practice).
- (15) Participants will receive \$25 for phlebotomy, \$50 for oral cancer screening and \$50 for follow-up Dental Visit (detailed survey + oral rinse), for a total of \$125.

5.3.3.2 Retention

Retention will apply to a small minority of study participants (anticipated to be approximately 25 patients) enrolled in the 6-month follow-up study.

The CC will work with the Regional Administrative Sites (RAS), study patients and dental providers to coordinate appointments for the follow-up dental visit, blood draw and oral cancer screening examination. The RC may conduct reminder telephone calls for research visits to ensure protocol compliance and patient retention.

5.4 **Subject Withdrawal**

5.4.1 ***Reasons for Withdrawal***

Patients are free to withdraw from participation in the study at any time upon request.

An investigator may terminate a study patient's participation in the study if:

- (1) Any clinical adverse event (AE), laboratory abnormality, or other medical condition or situation occurs such that continued participation in the study would not be in the best interest of the patient.
- (2) The patient meets an exclusion criterion (either newly developed or not previously recognized) that precludes further study participation.

5.4.2 Handling of Subject Withdrawals

Withdrawn patients will not be replaced. In the case of patient withdrawal from the study, staff will only attempt continued follow-up data collection for patients who are withdrawn due to an unanticipated problem (UP). In those cases, only data related to the completion of reporting requirements for the UP will be recorded. Patients withdrawn from the study for any other reason will have the date and reason for withdrawal recorded, but will not have any additional study data recorded. Although patients withdrawn from the study may continue to receive normal clinical care as patients of the participating dentists, additional study data will not be collected from this continuing clinical care (except as noted above).

5.5 Premature Termination or Suspension of Study

This study may be suspended or prematurely terminated if there is sufficient reasonable cause. Written notification, documenting the reason for study suspension or termination, will be provided by the suspending or terminating party. If the study is prematurely terminated or suspended, the Grant Principal Investigator (GPI) will promptly inform the IRB and will provide the reason(s) for suspension or termination.

Circumstances that may warrant termination include, but are not limited to:

- (1) Determination of unexpected, significant, or unacceptable risk to patients.
- (2) Insufficient adherence to protocol requirements.
- (3) Data that are not sufficiently complete and/or evaluable.

6 STUDY SCHEDULE

6.1 Dental Practitioner and Head and Neck Specialist Preparation and Training

The study will proceed in stages:

- (1) Dental practitioners at approximately 30 practice locations are assessed for interest in the study.
- (2) Head and Neck Specialists are assessed for interest in the study, such that each participating practice location will have coverage by an interested specialist.
- (3) IRB submission, approval and verification of the study protocol and its appendices are completed.
- (4) Dental practitioners and participating Head and Neck Specialists are recruited, receive necessary IRB training, and sign and submit (mail or in-person) the practitioner informed consent form (Appendix N; if required by that region's IRB), Individual Investigator Agreements, University of Alabama at Birmingham (UAB) Master Service Agreement, and similar regulatory documents.
- (5) Practitioners are fully informed of and review the electronic oral HPV and oral cancer risk factor surveys (Appendices C and K) in their entirety.
- (6) Practitioners, dental practice staff, and Head and Neck Specialists are trained on study procedures, including operation of the web-application, administration of questionnaires, and collection of oral rinse specimens. RCs facilitate this training remotely (webinar) or on-site, as regionally determined.
- (7) Practitioners and specialists are trained to answer questions regarding oral HPV and counsel high-risk HPV-positive patients. RCs facilitate this training remotely (webinar) or on-site, as regionally determined.
- (8) Specific roles and responsibilities of the practitioners and their staff are determined according to their site-specific workflow and documented by the RC.
- (9) RCs complete the Site Initiation Checklist (see MOP) prior to study initiation to ensure that practitioners are properly equipped to perform study procedures.
 - a. RC/CC delivers a refrigerator/freezer (if necessary), wireless router (if necessary), tablet computer, specimen collection kits and shipping supplies to appropriate locations.
- (10) Practitioners begin patient enrollment.

6.2 Patient Study Enrollment Schedule

A Study Schedule of Events is provided as Appendix D. The following sections detail the major events that will occur at each visit. There will be some flexibility to complete certain events in the order that is most convenient for staff workflow.

6.2.1 Part I, Oral HPV Screening

Patient Enrollment and Screening (Visit 1, Day 0)

Location: Dental practitioner's office or clinic

1. Verify eligibility via web application;
2. Obtain consent via web application (Appendix A);
3. Administer electronic oral HPV risk factor survey via web application (Appendix C).
 - a. If patient is **not selected** by the web-application for oral rinse sample (approximately 64.1% of patients), a practice staff member will notify the patient that his or her **involvement in the study is complete**.
 - b. If patient is **selected** by the web-application for oral rinse sample (approximately 35.9% of patients); **continue through Visit 1, steps 4-5**.
4. Obtain participant contact information via web application;
5. Obtain oral rinse sample (done by dentist, dental hygienist or dental assistant); oral rinse samples are stored at 4°C, then shipped in batches to study laboratory by practice staff approximately once or twice a week.
6. Once the patient's oral rinse sample is received by the HPV detection laboratory (Polaris Innovation Centre), results will be communicated to dental practitioners within approximately 5 business days via the secure web application.
 - a. If patient has a **negative** high-risk oral HPV test result (anticipated to be approximately 33.4% of patients), proceed to **Visit 2A**; or
 - b. If a patient has an oral rinse sample that is not evaluable, proceed to **Visit 2B**; or
 - c. If patient has a **positive** high-risk oral HPV test result (anticipated to be approximately 2.5% of patients), proceed to **Visit 2C**.

HR-HPV Results Notification – Negative (Visit 2A: Day 14, -11 days to +5 business days)

Location: Telephone

1. Using an approved script (Appendix E), the dentist notifies the patient of their negative high-risk oral HPV test result and explains that their involvement in the study is now complete.

HR-HPV Results Notification – Not Evaluable (Visit 2B: Day 14, -11 days to +5 business days)

Location: Telephone

1. Using an approved script (Appendix G), the dentist notifies the patient that their oral rinse was deemed “not evaluable” by the study laboratory and the high-risk oral HPV test could not be conducted.
2. The caller will then invite the patient to schedule a visit at the dental office to recollect the oral rinse sample that can be sent for evaluation of high-risk HPV.

HR-HPV Results Notification – Positive (Visit 2C: Day 14, -11 days to +5 business days)

Location: Telephone

1. Using an approved script (Appendix F), the dentist notifies the patient that they have a positive high-risk oral HPV test result and explains that a RC will call them with a detailed explanation of the follow-up portion of the study.

6.2.2 Part II, Oral Cancer Screening (Follow-Up Study)

Follow-up Enrollment (Visit 3; Day 16, -12 days to + 7 days)

Location: Telephone

1. Using an IRB-approved script (Appendix H), the RC provides a detailed explanation of the follow-up study to the patient, answers questions and potentially obtains telephone consent.

Intermediate Visit – Blood Draw (Visit 4; Month 6, -5 months to +2 months)

Location: The blood draw location will be determined by the RC and dental practice on a site-by-site basis. Options include clinical laboratory, community hospital, mobile phlebotomy service, participating Head and Neck Specialist's office or a participating dental practice capable of drawing blood.

1. The phlebotomist obtains a blood serum sample, using a CC-provided, pre-labeled blood sample collection kit.
2. The blood serum sample is shipped by the collaborating blood-draw location overnight to the study laboratory at the Ohio State University, using the CC-provided, pre-printed, prepaid shipping materials.

Intermediate Visit – Oral Cancer Screening Examination (Visit 5; Month 6, -5 months to +2 months)

Location: Participating Head and Neck Specialist (Otolaryngologist or Oral-maxillofacial Surgeon) clinic

1. Licensed, participating Head and Neck Specialist conducts a comprehensive head and neck exam.

Final Study Visit (Visit 6; Month 6, -1 month to +3 months)

Location: Dental practitioner's office or clinic

1. Oral cancer risk factor survey administered via web application (Appendix J);
2. Dentist, dental hygienist, or dental assistant obtains repeat oral rinse sample; oral rinse samples are stored at 4°C, then shipped in batches to study laboratory by practice staff once or twice a week;
3. If blood sample is collected at Visit 6, sample collection and shipping procedures will be same as mentioned for the blood draw at the Intermediate Visit (Visit 4).

HR-HPV Results Notification – Negative (Visit 7A: Visit 6 +14 days, -11 days to +5 days)

Location: Telephone

1. Using an approved script (Appendix E), the dentist notifies the patient of their negative high-risk oral HPV test result and explains that their involvement in the study is now complete.

HR-HPV Results Notification – Not Evaluable (Visit 7B: Visit 6 +14 days, -11 days to +5 days)

Location: Telephone

1. Using an approved script (Appendix H), the dentist notifies the patient that their oral rinse was deemed “not evaluable” by the study laboratory and the high-risk oral HPV test could not be conducted.
2. The caller will then invite the patient to schedule a visit at the dental office to recollect the oral rinse sample that can be sent for evaluation of high-risk HPV.

HR-HPV Results Notification – Positive (Visit 7C: Visit 6 +14 days, -11 days to +5 days)

Location: Telephone

1. Using an approved script (Appendix F), the dentist notifies the patient that they have a positive high-risk oral HPV test result and provides appropriate education and counseling.
2. The dentist may ask the patient if they are interested in being contacted regarding participation in a future study that will monitor for persistent HPV infection.
3. The dentist notifies the patient that their involvement in the follow-up study is complete.

6.3 Practitioner and Staff Survey

Once a practice location has completed patient enrollment and all patient follow-up procedures, each practice staff member will be asked to complete the Provider Survey (Appendix P) to collect information on the feasibility and acceptability of study procedures among dental office staff.

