- Précis:** A target of 1,000 men and women aged 30-69 years will be enrolled over a 6-month period, with up to 1,200 enrollments allowed to avoid cutting off enrollment in the middle of a business day. Approximately thirty practice locations will be recruited from the 6 National Dental PBRN regions (approximately 5 practice locations per region). Approximately 40 practitioners will be recruited among the approximately 30 practice locations. Participating patients will be recruited during routine clinical visits with participating National Dental PBRN practitioners. Each practitioner will recruit approximately 25-50 patients. Patients will be provided a tablet computer on which the study will be explained, electronic consent will be obtained, patient eligibility will be assessed, an oral HPV risk factor survey will be administered, and patient selection for oral rinse collection will be determined. Based on survey responses, the top three deciles of risk (~300) and a random selection of 1 in 12 of those in the lower deciles (~59) will be selected for oral rinse collection (~359 total). An oral rinse sample will be obtained by means of a 30 second rinse and gargle with Scope™ mouthwash (or saline), expectorated into a sterile specimen collection cup, sealed and stored at 4°C. Specimens will be shipped by practice staff approximately weekly or twice a week to a central laboratory for human papillomavirus (HPV) detection. HPV results will be communicated to the dental practitioner through the study's secure web application. Patients with a high-risk oral HPV infection (anticipated to be ~25 individuals) will be offered enrollment into a prospective study inclusive of a blood draw, an oral cancer examination, and a 6-month follow-up dental visit (window: 5-9 months) with a repeat oral rinse and an electronic oral cancer risk factor survey. Patients will be compensated with a gift card for each major study procedure.
- Objectives:** The primary objective of this study is to estimate the proportion of the study population with an oral high-risk HPV infection.
- The secondary objectives of this study are to:
- (1) Evaluate the feasibility and acceptability of baseline study procedures performed by participating patients and staff;
 - (2) Measure the distribution of demographic and behavioral

characteristics associated with oral HPV infection;

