3.2 Study Outcome Measures

The primary study outcome measure is the proportion of the study population with an oral high-risk HPV infection, which will be assessed through laboratory testing of the oral rinse specimen, recorded on a laboratory testing electronic Case Report Form (eCRF).

Secondary study outcome measures corresponding to the secondary objectives noted above will include:

- (1) The feasibility and acceptability of baseline study procedures performed by participating patient and dental office staff as assessed through:
 - a. Patients:
 - i. Electronic study summary (Appendix A): proportion of patients who agree to learn more about the study; proportion of patients who screen eligible to participate; proportion of patients who agree to the electronic consent.
 - ii. Oral HPV risk factor survey (Appendix C): acceptability of questions about risk factors ascertained in the survey.
 - b. Dental office staff:
 - i. Practitioner acceptability: Practitioners approached to participate in the study, those who agree or decline participation during the consent process, and practitioners who complete study-specific training.
 - ii. Feasibility (protocol education/training; patient recruitment; patient consent; answering questions; collecting, storing, and shipping oral rinses; distributing gift cards; providing test results).

-
- iii. Provider survey (Appendix P): ascertains acceptability (acceptability of extra time required for study procedures; comfort with study procedures; interest in participating in a future study) among practice staff.
- (2) The distribution of demographic and behavioral characteristics associated with oral HPV infection as assessed by the oral HPV risk factor survey (Appendix C) (gender; age; race/ethnicity; marital status; education; cigarette smoking; lifetime number of sexual partners) stratified by oral HPV status (laboratory testing eCRF).
- (3) The compliance with and feasibility of procedures done at the 6-month follow up visit performed by participating patients and dental office staff as assessed through:
- a. Patients:
 - i. eCRFs completed by the Regional Coordinator (RC), and will include a proportion of individuals with oral high-risk infection who: (a) enroll in the prospective study; (b) attend a 6-month follow-up; (c) undergo phlebotomy; (d) undergo ENT exam; and (e) complete the Oral Cancer Risk Factor Survey (Appendix J).

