 - (2) The dentist may refer the patient to a trained RC (one from each region) if the patient has questions that need to be addressed; and
 - (3) If necessary, the RC may refer the patient to the SPI, [name] to address additional questions, as needed (pilot study only).

- Patients with a high-risk oral HPV infection determined from the oral specimen (anticipated to be about 25 patients) will be eligible for a prospective study. Soon after patients are informed of their high-risk oral HPV infection, an RC will contact them about the prospective study which includes a 6-month blood draw (window: 1 to 8 months), 6-month oral cancer screening examination (window: 1 to 8 months), and a 6-month follow-up visit at the dentist office that will consist of a repeat oral rinse and electronic oral cancer risk factor survey (Appendix J; window: 5-9 months). Consent (Appendix I) and enrollment will be conducted by the RC via telephone. RCs will facilitate scheduling of appointments for the prospective study procedures.

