11.3 Final Analysis Plan

To accomplish the primary objective, our outcomes of interest will be the number of individuals determined to be in the top three deciles of risk based on our model (i.e., those selected for oral sample collection based on risk) as well as the proportion of those individuals with an oral high-risk HPV infection. Based upon our model in NHANES, we would expect that 30% of the participating population would be selected for specimen collection and that the resulting population would have an oral high-risk prevalence of 8.43% (95%CI 6.68% to 10.14%). The number of individuals selected as high-risk will be informative with regard to the distribution of

risk factors in the study population, and the proportion positive will be informative with regard to the β -estimates for our risk model.

Shown in the table below are the upper and lower bounds of the 95% CI for the proportion positive for oral high-risk HPV infection, assuming a range of 10-50% of the study population is categorized as high-risk based on our model. A proportion of the study population with oral high-risk infection that falls within the confidence bounds in the table below, given the sample size, will indicate that the β -estimates in our NHANES model are reasonable estimates of risk to the study population.

Sample size	Proportion	95% Confidence Interval	
		Lower Bound	Upper Bound
100	8.43%	2.98%	13.88%
200	8.43%	4.58%	12.28%
300	8.43%	5.29%	11.57%
400	8.43%	5.71%	11.15%
500	8.43%	5.99%	10.87%

To accomplish secondary objectives (1) and (3) a brief Provider Survey (Appendix P) will be administered via tablet computer/web-application to providers at each participating practice to assess acceptability of each procedure and willingness to participate in a future larger study. Results will be reported as summary statistics.

Descriptive statistics for secondary objective (3) include the proportion of individuals with high-risk oral HPV infection who:

- (1) Enroll in the follow-up study;
- (2) Attend a 6-month follow-up;
- (3) Provide blood serum sample; and
- (4) Provide second oral rinse.

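### The Provider Survey waits until a practice has finished enrolment and all follow-up, which leaves no survey point for a practice that withdraws and makes recall time for baseline procedures differ between practices

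*Protocol*

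**What the plan says.** Section 6.3 ties the survey to completion: "Once a practice location has completed patient enrollment and all patient follow-up procedures, each practice staff member will be asked" to complete it. No other section gives a time.

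Section 11.3 assigns the same instrument to two objectives: "To accomplish secondary objectives (1) and (3) a brief Provider Survey (Appendix P) will be administered via tablet computer/web-application". It goes "to providers at each participating practice to assess acceptability of each procedure and willingness to participate in a future larger study". Section 3.2 also lists the survey under both objectives, with the same acceptability topics each time: extra time, comfort with the procedures, and interest in a future study.

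Only patients positive for high-risk HPV have follow-up. Section 5.3.3.2 puts their number low: "Retention will apply to a small minority of study participants (anticipated to be approximately 25 patients) enrolled in the 6-month follow-up study".

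Section 3.2 also records practitioner acceptability outside the survey, counting practitioners approached, "those who agree or decline participation during the consent process, and practitioners who complete study-specific training".

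**The concern.** Feasibility and acceptance are in the study title, in secondary objectives 1 and 3 and in hypotheses 2 and 5. Section 11.3 says the pilot will assess whether the procedures can be built into clinical practice, ahead of a future study of 60,000 screened individuals. The Provider Survey is the named source of acceptability ratings from the staff who do the work.

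Two features of the trigger weaken it:

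- **Practices that stop.** A practice that withdraws after trying recruitment, rinse collection, shipping or result calls does not complete enrolment and follow-up. Its staff are among those most likely to have found the procedures burdensome.
- **Unequal recall.** Whether staff are asked about baseline work within weeks or after many months depends on whether their practice happened to have a patient in follow-up.

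Both concern which data are collected and when. An analysis plan cannot later recover ratings that were never requested, or shorten the recall interval.

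**Working it through.** **1. The plan's own figure.** Sections 4 and 5.3.3.2 expect about 25 positives. The Protocol Summary puts about 300 patients in the top three risk deciles, and section 11.3 expects 8.43% of them to be positive: 300 × 0.0843 = 25.3. Section 6.2.1 gives 2.5% of patients: 0.025 × 1,000 = 25. The figure reproduces.

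**2. Practices with no follow-up patient.** Inputs are 25 positives and about 30 practices (section 4), or 25/30 = 0.83 per practice. Assume equal practices, random allocation and full uptake of follow-up.

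- P(no positive in a practice) = (29/30)^25 = 0.428.
- Expected practices with none: 30 × 0.428 = 12.9, about 13.
- Expected practices with at least one: 30 − 12.9 = 17.1, about 17.

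Sensitivity (uptake, total positives and intraclass correlation are assumptions):

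| Scenario | Practices with none | Practices with at least one |
|---|---|---|
| 15 positives, or 25 with 60% uptake | 18.0 | 12.0 |
| 20 positives, or 25 with 80% uptake | 15.2 | 14.8 |
| 25 positives, full uptake | 12.9 | 17.1 |
| 30 positives | 10.8 | 19.2 |
| 35 positives | 9.2 | 20.8 |
| Clustering by practice, ICC 0.02 (simulated) | 15.8 | 14.2 |
| Clustering by practice, ICC 0.05 (simulated) | 18.4 | 11.6 |

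The simulated rows use 33 patients per practice (1,000/30) and 2.5% positive.

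**3. Delay in practices with a follow-up patient.** Section 6.2.2 sets Visit 6 at month 6, −1 to +3 months, so month 5 to month 9. Result notification (Visit 7) is 14 days later, −11 to +5 days, so 3 to 19 days after Visit 6. Counting Visit 7 as part of follow-up:

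- Earliest: 5 months + 3 days ≈ 5.1 months after that patient's baseline visit.
- Latest: 9 months + 19 days ≈ 9.6 months.

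Without Visit 7 the range is 5 to 9 months. The last follow-up patient in a practice sets its survey date. If a practice enrolled for the full 6 months that section 5.3.3.1 allows, and its last patient was positive, its first baseline visit could lie 6 + 9.6 = 15.6 months back. Enrolment may be much shorter: section 4 gives about five weeks per practitioner as an example.

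**4. Delay in the other practices.** With no follow-up outstanding, the trigger is met once enrolment is closed, and staff can be asked soon afterwards.

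**5. Practices that stop.** Set side by side, section 6.3 requires completion, while section 11.3 addresses every participating practice. Section 5.4 covers withdrawal of patients, not of practices. No section says when a withdrawing practice would be surveyed.

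**The case against.** The case on the other side has real weight.

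- **Intent.** A reader might infer that the survey is limited to completers by design. Section 11.3 does not support that, since it addresses each participating practice. What stands is a mismatch between the two sections, and only 6.3 says when to ask.
- **Low enrolment.** A reader might also infer that practices that enrol poorly are missed. Sections 4 and 5.3.3.1 close enrolment centrally, within about 48 hours of reaching 1,000 patients. A practice below its target can therefore still reach the trigger. The gap concerns practices that withdraw.
- **Other records.** Agreement, refusal and training completion are recorded (section 3.2), as are enrolment by practitioner and attrition by practice (section 15.4). The first three precede any study procedure, and the reports count patients. None replaces the ratings of staff who tried the procedures and stopped.
- **Objective 3.** A reader might conclude that staff without a follow-up patient rate work they never did, and that the objective 3 staff result has no meaning. The protocol does not show this. The content of Appendix P is not given, and it may offer a not-applicable answer or separate items. In section 3.2, every objective 3 staff task except patient retention also appears in the baseline list. The examination is done by a specialist, and the blood is often drawn elsewhere.
- **Design preference.** One short survey at the end of participation is defensible in a descriptive pilot whose primary objective is HPV prevalence. That limits the weight of the point but does not remove the missing survey point or the unequal recall.

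**Conclusion.** The point holds in a limited form. Read literally, section 6.3 gives no survey point for staff at a practice that withdraws, and it should be reconciled with section 11.3. Recall of baseline procedures also differs systematically. It runs about 5 to 9.6 months from the follow-up patient's baseline visit in about 17 of 30 practices, and is much shorter in about 13. The long delay and the absence of follow-up experience therefore affect different practices, and no practice has both.

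The 17 and 13 rest on 25 positives, equal practices, random allocation and full uptake. Across the scenarios above, practices with a follow-up patient range from about 12 to 21.

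A reader might infer that staff acceptability will be overstated by some definite amount. The direction is plausible if practices that stop are less satisfied. However, the protocol gives neither an expected practice withdrawal rate nor expected ratings, so no size can be stated. The primary objective is not affected. This is a cheap improvement to a secondary objective that is central to the pilot.

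**What to change.** In section 6.3:

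- Administer the survey when a practice closes enrolment or stops participating, whichever comes first.
- Ask the follow-up items after the last follow-up visit, only in practices with at least one follow-up patient.

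In section 11.3:

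- State the same timing, so that it agrees with the intention to survey every participating practice.
- Base the objective 3 staff acceptability results on the practices that had follow-up patients.

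The cost is a small amendment and a second survey in about 17 practices (about 12 to 21 over the scenarios above). Section 7.4.1 puts the whole 19-question survey at 3 to 6 minutes, so a follow-up part should take no longer than that.
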